8.2 SAFETY

Patients will be evaluable for safety if they receive at least one (complete or incomplete) dose of PM060184.

Safety will be evaluated by clinical examinations, analysis of vital signs, clinical assessment of AEs, changes in the analytical parameters (hematological and biochemical), and any other analyses that may be considered necessary.

All treatment-related AEs must be followed-up—even if the administration of PM060184 has finalized—until the AE or its sequelae have resolved or stabilized at an acceptable level to the Investigator and the Sponsor. AEs will be graded according to the National Cancer Institute Common Terminology Criteria for Adverse Events (NCI-CTCAE v.4), and will be coded using the Medical Dictionary for Regulatory Activities (MedDRA).

8.3 PATIENT REPORTED OUTCOMES

EORTC QLQ-CIPN20 and QLQ-C30 will be used to collect information on patients' self-reported QoL and neurotoxicity, targeting symptoms, functional limitations, and patient concerns specifically associated with treatment-induced PN, and potential activity impairment.

Patients will be asked to complete both QLQs at baseline, on Day 8 of each cycle, at the end-of-treatment visit.

Patients will be asked to complete the QLQ-CIPN20 (only) during the follow-up period (about every three months until start of subsequent antitumor therapy). If a patient discontinues treatment due to grade ≥ 3 PN, however, the QLQ-CIPN20 should be completed more frequently during the follow-up period (every month after EOT) until recovery to grade ≤ 2 (or until start of subsequent antitumor therapy).

8.4 ADVERSE EVENTS

An AE is any untoward medical occurrence in a patient or clinical investigation patient administered a pharmaceutical product which does not necessarily have a causal relationship with this treatment.

An AE can therefore be any unfavorable and unintended sign, (e.g., an abnormal laboratory finding), or a disease temporally associated with the use of a medicinal product, whether or not considered related to the medicinal product.

Illnesses with onset during the study or exacerbations of pre-existing illnesses, including but not limited to clinically significant changes in physical examination findings and abnormal objective test findings (e.g., X-ray, ECG) should be recorded. The criteria for determining whether an abnormal objective test finding should be reported as an AE are as follows:

- The test result is associated with clinically significant symptoms, and/or
- The test result leads to a change in the study dosing or discontinuation from the clinical trial, significant additional concomitant drug treatment or other therapy, and/or
- The test result leads to any of the outcomes included in the definition of a SAE (see definition below), and/or
- The test result is considered to be clinically relevant by the Investigator.

For the purposes of this protocol, disease progression, worsening of the underlying disease or appearance of new tumor lesions, or any sign or symptom clearly related with this circumstance is NOT required to be reported as an AE.

8.4.1 Serious Adverse Event (SAE)

A SAE is any adverse experience occurring at any dose that:

- Results in death (is fatal),
- Is life-threatening,
- Requires or prolongs inpatient hospitalization,
- Results in persistent or significant disability or incapacity,
- Is a congenital anomaly or birth defect,
- Is medically significant, or
- Is any suspected transmission of an infectious agent via a medicinal product.

Medical and scientific judgment should be exercised in deciding medically significant events; this criterion should be applied to AEs that may not be immediately life-threatening or result in hospitalization but may jeopardize the patient or may require intervention to prevent one of the outcomes listed in the above definition.

8.4.2 Death

Death as such is the outcome of a SAE and should not be used as the SAE term itself, whenever possible. The cause of death should be recorded as the SAE term instead. When available, the autopsy report will be provided by the Sponsor.

8.4.3 Life-threatening Event

Any event in which the patient was at risk of death at the time of the event is considered life-threatening; it does not refer to an event which hypothetically might have caused death if it were more severe.

8.4.4 Hospitalization or Prolongation of Hospitalization

Any AE requiring hospitalization (or prolongation of hospitalization) that occurs or worsens during the course of a patient's participation in a clinical trial must be reported as a SAE unless exempted from SAE reporting. Prolongation of hospitalization is defined as any extension of an inpatient hospitalization beyond the stay anticipated/required for the initial admission, as determined by the Investigator or treating physician.

Hospitalizations that do not meet the criteria for SAE reporting are:

- a. Reasons described in the protocol (e.g., IMP administration, protocol-required intervention/investigations, etc.). However, events requiring hospitalizations or prolongation of hospitalization as a result of a complication of therapy administration or clinical trial procedures will be reported as SAEs.
- b. Hospitalization or prolonged hospitalization for technical, practical or social reasons, in the absence of an AE.
- c. Pre-planned hospitalizations: any pre-planned hospitalization, surgery or procedure must be documented in the source documentation. Only if the pre-planned hospitalization, surgery or procedure needs to be performed earlier due to a worsening of the condition, should this event (worsened condition) be reported as a SAE.

Other situations that **MUST NOT** be considered as hospitalizations are the following:

- d. An emergency visit due to an accident where the patient is treated and discharged.

- e. When the patient is held 24 hours for observation and finally is not admitted.
- f. Planned treatments at sites not associated to a hospital and generally considered as minor surgical procedures (i.e., laser eye surgery, arthroscopy, etc.).

8.4.5 Unlisted/Unexpected Adverse Event

An AE, the nature or severity of which is not consistent with the applicable reference safety information.

The Sponsor will use as the reference safety information for the evaluation of listedness/expectedness the IB for PM060184.

8.4.6 Adverse Reactions

All untoward and unintended responses to an investigational medicinal product related to any dose administered. This definition covers also medication errors and uses outside what is foreseen in the protocol, including overdose, lack of efficacy, misuse and abuse of the product.

8.4.7 Adverse Events Related to the Study Drug

An AE is considered related to a study drug/IMP if the Investigator's assessment of causal relationship to the IMP(s) is "Y (yes)" (see Section [8.4.9](#)).

The Investigator will assess the causal relationship of the IMP(s) to the AE.

The Sponsor may also consider related to the study drug(s)/IMP(s) those events for which the Investigator assesses the causal relationship with the IMP(s) as "Uk (unknown)" when it cannot rule out a role of the IMP(s) in the event.

8.4.8 Expedited Reporting

The Sponsor is responsible for the appropriate expedited reporting to the Competent Authorities, Investigators, and IECs/IRBs according to the current legislation, unless otherwise required and documented by the IECs/IRBs.

8.4.9 Assessment of Causal Relationship to the Study Drug

The Investigator must provide an assessment of the causal relationship of each clinical trial IMP(s) to each SAE according to the following scale:

- Y** There is a reasonable possibility that the IMP(s) caused the SAE.
- N** There is no reasonable possibility that the IMP(s) caused the SAE and other causes are more probable.
- Uk.** (Unknown). Only to be used in special situations where the Investigator has insufficient information (i.e., the patient was not seen at his/her center) if none of the above can be used.

8.5 ADVERSE EVENTS REPORTING PROCEDURES

8.5.1 Reporting Adverse Events

The Sponsor will collect AEs until 30 days after administration of the last dose of study drug(s)/IMP(s) or until the start of a new antitumor therapy, whichever occurs first. All AEs suspected to be related to the study drug/IMP must be followed-up after the time of therapy discontinuation until the event or its sequelae resolve or stabilize at an acceptable level to the Investigator and the Sponsor.

All AEs, including misuse, overdose, abuse and medication error, must be recorded in English using medical terminology in the source document and the e-CRF. Whenever

possible, the Investigator will record the main diagnosis instead of the signs and symptoms normally included in the diagnoses.

Investigators must assess severity (grade) of the event following the NCI-CTCAE v.4 and assign a relationship to each study drug(s)/IMP(s); and pursue and obtain information adequate both to determine the outcome and to assess whether it meets the criteria for classification as a SAE requiring immediate notification to the Sponsor or its designated representative. The Investigator must provide any relevant information as requested by the Sponsor in addition to that on the e-CRF.

Abnormal laboratory tests occurring during the study must only be recorded in the AE section of the e-CRF if the disorder:

- is associated with clinically significant symptoms, and/or;
- represents a reason for change in study dosing or for discontinuation from the study treatment, significant additional concomitant drug treatment or other therapy, and/or;
- leads to any of the outcomes included in the definition of a SAE.
- it is considered clinically relevant by the Investigator.

Otherwise, laboratory results should be reported in the corresponding section of the e-CRF (e.g., biochemistry, hematology).

8.5.2 Reporting Serious Adverse Events

The Sponsor will collect SAEs from the time of signing of the ICF until 30 days after administration of the last dose of study drug/IMP or until the start of a new antitumor therapy, whichever occurs first (or until screening failure, if applicable). Beyond this period of time, only those SAEs suspected to be related to the IMP will be collected. Nonetheless, the Sponsor will evaluate any safety information that is spontaneously reported by an Investigator beyond the time frame specified in the protocol.

All SAEs (as defined above) occurred after patient registration regardless of relationship to the study drug(s)/IMP(s) must be reported immediately, and always within 24 hours to the Pharma Mar S.A. Pharmacovigilance Department, electronically by completing the applicable e-CRF section.

SAEs occurring during the screening phase, SAEs that may occur off-study, or in case the electronic system fails or is not available, will be reported within 24 hours to the Pharmacovigilance Department using the paper SAE form by fax ([contact]), e-mail ([contact]) or telephone ([contact]).

Out of office hours [Greenwich Meridian Time (GMT)], assistance on SAE reporting can be obtained by calling the Pharmacovigilance Department at [contact]. SAEs initially reported by alternative methods (not electronically), must be followed by a completed electronic SAE reporting on e-CRF from the investigational staff within one working day.

All SAEs suspected to be related to the IMP(s) must be followed until the event or its sequelae resolves or stabilizes at an acceptable level by the Investigator.

8.5.3 Reporting Pregnancy Cases Occurred within the Clinical Trial

National regulations require that clinical trial Sponsors collect information on pregnancies occurring during clinical trials, in which exposure to the IMP(s) at any time during pregnancy, via either maternal or paternal exposure, is suspected.

Therefore, pregnancy and suspected pregnancy (including a positive pregnancy test regardless of age or disease state) of a female patient or the female partner of a male patient occurring while the patient is on study drug, or within six months in female patients and within four months in male patients after the last study drug administration, are considered immediately reportable events.

The Investigator will report the following events immediately and always within 24 hours from first knowledge:

- Any occurrence of a pregnancy where any kind of exposure to the IMP(s) is suspected.
- Possible exposure of a pregnant woman (this could involve a partner of a male patient or a pregnant female who came in contact with the clinical trial IMPs).
- All reports of elevated/questionable or indeterminate beta human chorionic gonadotropins (β -hCGs).

Immediately after detecting a case of suspected pregnancy in a female clinical trial patient, the decision on her continued participation in the clinical trial will be jointly taken by the trial patient, the Investigator and the Sponsor, with the patient's best interest in mind. A decision to continue the pregnancy will require immediate withdrawal from the trial.

Any pregnancy, suspected pregnancy, or positive pregnancy test must be reported to Sponsor Pharmacovigilance immediately by facsimile using the Pregnancy Report form. In the case of pregnancy of the female partner of a trial patient, the Investigator will obtain her informed consent to provide the information by using the applicable form provided by the Sponsor who will also advise the Investigator in these situations.

The Investigator will follow the pregnancy until its outcome, and must notify PharmaMar Pharmacovigilance of the outcome of the pregnancy within 24 hours of first knowledge as a follow-up to the initial report.

For any event during the pregnancy which meets a seriousness criterion (including fetal or neonatal death or congenital anomaly) the Investigator will also follow the procedures for reporting SAEs (complete and send the SAE form to PharmaMar Pharmacovigilance by facsimile within 24 hours of the Investigator's knowledge of the event).

All neonatal deaths that occur within 30 days of birth should be reported, without regard to causality, as SAEs. In addition, any infant death at any time thereafter that the Investigator suspects is related to the exposure to the study drug(s)/IMP(s) should also be reported to PharmaMar Pharmacovigilance by facsimile within 24 hours of the Investigators' knowledge of the event.

8.5.4 Adverse Events Monitoring

Safety review will be performed by the Sponsor once SAE forms have been received electronically or by fax and the e-CRFs have been electronically completed by the Investigator.

Periodic safety review of clinical data will be performed; however, no formal Data Safety Monitoring Board has been appointed for this trial. AEs will be monitored by the Investigators and by the Sponsor study team. The personnel in charge of this process are listed in the Study Contacts section of this protocol. In general, the clinical oncologist medical monitor together with the PharmaMar Pharmacovigilance Department will review the safety data of this trial on an ongoing basis.

SAEs will be collected, assessed and reported as per the applicable Regulations by the Pharmacovigilance Department. Periodic safety reviews of SAE reports are to be conducted by the Pharmacovigilance Department every 3–6 months, depending on recruitment.

Non-serious AEs will be verified during monitoring visits by the monitor, who will discuss them with the Investigators, if applicable.

At every monitoring visit the consistency between the e-CRF/SAE data reported to the Pharmacovigilance Department and the patient's source data will be reviewed. When a discrepancy is found, data in the e-CRF and the SAE form/information will be amended/updated and reported to the Pharmacovigilance department (when applicable), according to source data.

9. STATISTICAL METHODS

9.1 PRIMARY ENDPOINT

Progression-free survival rate at 12 weeks (PFS3), defined as the rate estimate of the percentage of patients who are alive and progression-free at 12 weeks (~3 months) after the first treatment administration.

9.2 SECONDARY ENDPOINTS

- Overall Survival (OS), defined as the time from the first day of treatment to the date of death or last contact.
- Progression-free Survival (PFS), defined as the time from the first day of study treatment to the day of assessment of progression, death or last tumor evaluation.
- Overall Response Rate (ORR), defined as the percentage of patients with objective response (OR), either complete response (CR) or partial response (PR) according to the RECIST v.1.1.
- Duration of Response (DOR), defined as the time between the date when response criteria (PR or CR, the first to be reached) are fulfilled and the first date when PD, recurrence or death is objectively documented.
- Treatment safety, including AEs, SAEs, and laboratory abnormalities graded according to NCI-CTCAE v.4. Dose reductions or delays required due to treatment-related AEs, and reasons for treatment discontinuations will also be analyzed.
- Profiles of peripheral neuropathy and quality of life as reported by patients using the EORTC QLQ-CIPN20 and QLQ-C30.
- Pharmacokinetics (PK) parameters will be evaluated in plasma by population PK modeling and/or standard non-compartmental analysis.
- Metabolomics of PM060184, i.e., intra- and inter-patient systemic variations in the patient's pretreatment metabolic profile.
- Pharmacogenetics (PGt) of PM060184 will be evaluated to identify the presence or absence of germline mutations or polymorphisms that may help explain individual variability in the main PK parameters and safety outcomes.

- Pharmacogenomics (PGx) of PM060184 will be evaluated to determine predictive/prognostic markers of response and/or resistance to PM060184 (including BRAF-mutant-like gene expression subtypes).

9.3 SAMPLE SIZE

Patients will be treated with PM060184 to test the null hypothesis (H0) that 30% or less patients are alive and free of progression at twelve weeks (PFS3) according to RECIST v.1.1 ($p \leq 0.30$) versus the alternative hypothesis (H1) that 50% or more patients are alive and free of progression at 12 weeks according to the aforementioned criteria ($p \geq 0.50$). The variance of the standardized test is based on the null hypothesis. The type I error (alpha) associated with this one-sided test is 0.025 and the type II error (beta) is 0.1; hence, statistical power is 90%.

Sixty evaluable patients are necessary to test the hypothesis. A futility analysis using O'Brien-Fleming boundaries is planned when 24 patients can be evaluated (first stage). If there are seven or more patients achieving PFS3 in the first stage then the trial will proceed to a second stage and a total of 60 patients will be recruited.

If at least 25 of 60 evaluable patients are alive and free of progression at 12 weeks then the null hypothesis can be rejected and PM060184 considered active and deserving potential development in this setting.

9.4 STATISTICAL ANALYSIS

Frequency tables will be prepared for categorical variables and summary tables, including median, mean, standard deviation, minimum, and maximum values for each variable, will be used for continuous variables. Exploratory comparisons will be performed at a 0.05 level. Other analyses will include: number of prior treatment lines, prior oxaliplatin exposure, KRAS status, BRAF-like expression, and other prognostic/predictive factors.

9.5 EFFICACY ANALYSIS

The exact binomial estimator and its 95% confidence interval (CI) will be used for the primary endpoint (PFS3) and categorical variables (i.e., ORR). Time-to-event variables (DOR, PFS and OS) and their fixed time estimates will be analyzed according to the Kaplan-Meier method. For categorical variables, comparisons will be carried out by a Fisher exact test and a multivariate analysis by logistic regression. For time-to-event variables, comparisons will be carried out by a log-rank test and by a Cox regression analysis. No formal conclusions will be expected on these grounds.

9.6 SAFETY ANALYSIS

Safety analyses will consider AEs and SAEs, according to their relationship with study treatment, as well as analytical results, deaths and the reasons for treatment discontinuations, delays and/or dose reductions. All AEs and SAEs will be graded according to NCI-CTCAE v.4., and they will be coded using the MedDRA.

9.7 PATIENT REPORTED OUTCOMES

PRO analysis will be performed on summary measures and longitudinal modelling of patients' QLQ responses. QoL and PN will be evaluated by changes in the EORTC QLQ-CIPN20 and QLQ-C30 scores over time and tested for statistical significance by means of repeat-measure analyses of variance. The scores will be compared at the pre-specified time points using a T-test for related samples to establish differences, if any,

between pairs of assessments. A p-value of < 0.05 is considered statistically significant for the exploratory comparisons.

9.8 PHARMACOKINETICS ANALYSIS

Pharmacokinetic data will be listed in the population PK-report for all patients with available concentrations of PM060184. Patients will be excluded from the PK analysis if their data do not allow for accurate assessment of the PK (e.g. improper handling of PK samples, incomplete administration of the study agent, missing time or dosing information). All concentrations below the lowest quantifiable concentration or missing data will be labeled as such in the concentration data presentation. All patients and samples excluded from the analysis will be retained in the data set, but they will be flagged out and the criteria for the exclusion documented.

Population PK analysis of plasma concentration-time data of PM060184 will be performed using non-linear mixed-effects modeling. Data may be combined with those of a selection of phase I and II studies to support a relevant structural model. Available patient characteristics (demographics, laboratory variables, genotypes, etc.) will be tested as potential covariates affecting PK parameters. Details will be given in a population PK analysis plan and the results of the population PK analysis will be presented in a separate report.

Pharmacokinetic analysis will be the responsibility of the Sponsor and will be performed in accordance with the current guidelines on population pharmacokinetics analyses. Clearance and volume of distribution will be the primary parameters of interest for the population PK analysis. Additional PK parameters will be calculated, if deemed appropriate.

Non-compartmental PK analysis may also be used instead of or in addition to population PK analysis.

Plasma samples will be analyzed to determine concentrations of PM060184 using a validated, specific, and sensory liquid chromatography/mass spectrometry/mass spectrometry (LC-MS/MS) method by or under the supervision of the Sponsor.

9.9 METABOLOMICS (BIOMARKERS) ANALYSIS

Patients' pretreatment metabolic profile will be evaluated to search for systematic variations that may serve as biomarkers of PK, safety and/or efficacy response to treatment with PM060184. Systematic variations in the metabolic profile will be compared among patients with differences in any of these responses. Particular attention will be given to specific metabolic patterns observed in patients who develop PN associated with PM060184.

Metabolite extraction will be accomplished by fractionating the serum sample (19). Briefly, an ultra performance liquid chromatography (UPLC)-single quadrupole-MS amino acid analysis system will be combined with two separate UPLC-time-of-flight-MS based platforms analyzing methanol and chloroform/methanol serum extracts.

Data will be processed using the TargetLynx application manager for MassLynx 4.1 software (Waters Corp., Milford, USA). A set of predefined retention time and mass-to-charge ratio pairs (R_t - m/z), corresponding to metabolites included in the analysis will be fed into the program. Normalization factors will be calculated for each metabolite (20).

The metabolomics data analysis will include univariate and multivariate data analysis, with pathway mapping tools and visualization capacities to facilitate result interpretation.

Principal component analysis (PCA; non-supervised) and orthogonal partial least-squares to latent structures (OPLS; supervised) multivariate methods will be used to reduce the dimensionality of the complex data set to enable easy visualization of any metabolic clustering in samples from patients sharing a common outcome.

Among univariate data analysis, a Shapiro-Wilk test (to test the normality of data), a Student's t-test and a Wilcoxon signed-rank test, an analysis of variance (ANOVA) and a Tukey's HSD (Honestly Significant Difference) *post hoc* test will be used.

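### Protocol 9.9 seeks metabolite biomarkers of PK with univariate tests that are all group or paired comparisons; relating metabolites to clearance and volume as continuous values would gain power at no cost

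*Protocol*

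**What the plan says.** Biomarkers of PK are part of a secondary objective (Protocol section 3; SAP 3.2). Protocol 9.9 opens by saying that the "pretreatment metabolic profile will be evaluated to search for systematic variations that may serve as biomarkers of PK, safety and/or efficacy response", and then gives the form of the comparison: "Systematic variations in the metabolic profile will be compared among patients with differences in any of these responses".

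After a Shapiro-Wilk test of normality, the univariate tests are listed as "a Student's t-test and a Wilcoxon signed-rank test, an analysis of variance (ANOVA) and a Tukey's HSD (Honestly Significant Difference". The section names no univariate correlation or regression, no rule for grouping patients by PK, and no rank test for independent groups.

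The multivariate methods are PCA and OPLS, to be used "to enable easy visualization of any metabolic clustering in samples from patients sharing a common outcome".

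Protocol 9.8 says what PK means in this trial: "Clearance and volume of distribution will be the primary parameters of interest for the population PK analysis". SAP 8.9 specifies no metabolomics analysis and refers to a separate document, which is not among those reviewed.

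**The concern.** Clearance and volume have no natural groups. To put them through a t-test or an ANOVA, someone must divide patients into low and high, or into thirds, and 9.9 does not say where. That has two costs. Patients on the same side of the cut are treated as alike, which discards information in a small trial. The result also depends on a choice that is not fixed in advance. At stake is the sensitivity of one part of a secondary, exploratory objective.

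A smaller gap sits beside it. Patients with and without neuropathy, which 9.9 singles out, are independent groups. The only rank test named is the signed-rank test, which needs pairs. Normality is to be tested, but no independent-groups rank test is named for use when it fails.

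**Working it through.** Section 9.9 gives no sample size, power or significance level, so there is no stated figure to reproduce.

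**Inputs**
- Patients: 60 for the full trial, 24 if it stops after the first stage (Protocol 9.3). These are counts evaluable for PFS3. The number with usable metabolomics and PK data is not stated, so they serve as stand-ins.
- Significance level: 0.05 for exploratory comparisons (Protocol 9.4), taken here as two-sided.
- True correlation between metabolite and clearance: not in the documents. Assumed range 0.3 to 0.5, bivariate normal.
- Grouping: not in the documents. A median split and a three-way split are used as illustrations.

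**Step 1: hand check.** For bivariate normal data, a median split multiplies the correlation by √(2/π) = 0.798. For modest correlations it therefore keeps about 2/π = 64% of the information: 60 × 2/π = 38.2, so 60 patients act like about 38.

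Approximate power is Φ(atanh(r) × √(n − 3) − 1.96). With n = 60 and r = 0.40:
- Continuous: 0.4236 × 7.550 − 1.96 = 1.24, power about 89%.
- Median split: r becomes 0.40 × 0.798 = 0.319, and 0.3308 × 7.550 − 1.96 = 0.54, power about 70%.

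**Step 2: simulation.** 20,000 bivariate normal data sets per setting, two-sided 0.05:

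| n | Correlation | Pearson test | Median split, t-test | Three groups, ANOVA |
|---|---|---|---|---|
| 60 | 0.3 | 66% | 46% | 44% |
| 60 | 0.4 | 90% | 72% | 72% |
| 60 | 0.5 | 99% | 91% | 91% |
| 24 | 0.3 | 30% | 20% | 18% |
| 24 | 0.4 | 51% | 34% | 31% |
| 24 | 0.5 | 73% | 51% | 48% |

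The row for n = 60 and 0.4 agrees with the hand check. The median split loses 8 to 20 points at n = 60 (99 − 91; 66 − 46) and 10 to 22 points at n = 24 (30 − 20; 73 − 51). Three groups do no better overall.

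At a level of 0.001, an assumed allowance for testing many metabolites, n = 60 and 0.4 give 46% against 20%.

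**Step 3: is the t-test unsafe for skewed metabolites in independent groups?** 4,000 simulated lognormal data sets per setting, with log-SD 0.5 or 1.0 and groups of 30/30 or 50/10:
- Type I error of the t-test on raw values was 4.3% to 5.4%, so its size holds.
- Power for a shift of 0.8 SD on the log scale, 30/30, log-SD 1.0: t-test 69%, Mann-Whitney 85%, t-test on logs 87%.
- The same shift at 50/10: t-test 62% against Mann-Whitney 57% (log-SD 0.5), and 59% against 58% (log-SD 1.0).

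Strong skew therefore costs the t-test power in balanced groups but did not invalidate it in these settings.

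**The case against.** The case for leaving the text alone has four parts.

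1. **A regression-type method is already named.** OPLS is supervised and can take a continuous response. Protocol 9.8 also models PK on its own scale: "Available patient characteristics (demographics, laboratory variables, genotypes, etc.) will be tested as potential covariates affecting PK parameters". A reader might infer from the univariate list that no regression-type method is planned at all; the documents do not support that. But the stated purpose of OPLS in 9.9 is to show clusters of patients who share an outcome, and the open covariate list in 9.8 does not name metabolites. Continuous use is possible, not stated.

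2. **No split is prescribed.** This is correct. The protocol names no median, tertile or other cut for clearance, and the sentence on comparing patients covers safety and efficacy as well, where group tests suit categorical outcomes such as neuropathy. The power losses above therefore price a natural reading of the listed tests, not a written rule. The point stands because those univariate tests cannot be applied to a continuous response without some grouping.

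3. **The detail is deferred.** SAP 8.9 points to a separate document that cannot be checked here and may settle everything. That limits the point to the protocol text, which still says that the listed tests will be used.

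4. **The signed-rank test is not misplaced.** Samples are taken before dosing on Days 1 and 8 of Cycle 1 and Day 8 of Cycle 2 (Protocol 7.9), so within-patient change is a proper paired use. Section 9.9 never assigns the test to independent groups. A reader might go further and infer that non-normal metabolites have no valid group test. Step 3 does not bear that out, and a log transformation is not excluded. What remains is that no rank test for independent groups is named, although Protocol 9.10 names Mann-Whitney for its own comparisons. Alone, that would be only a missing detail.

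**Conclusion.** The point holds as a free improvement. Followed as written, the univariate part of 9.9 would group patients by a continuous PK parameter at an unstated cut and lose power. With a median split, the loss is 8 to 20 points at n = 60 and 10 to 22 points at n = 24. These figures rest on assumed correlations of 0.3 to 0.5, bivariate normality, a two-sided 0.05 level and data from every counted patient.

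A reader might conclude that real PK biomarkers will be missed. That is too strong: even after a median split, a correlation of 0.5 is found with 91% power at n = 60. The supported statement is lower power, together with dependence on an undeclared cut. PFS3, its decision rule and the primary conclusion are not affected.

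**What to change.** In Protocol 9.9 or the separate metabolomics plan, before metabolite data are linked to PK results:

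- **PK responses.** Relate each (log) metabolite to log clearance and log volume, or exposure, as continuous variables in all patients with data, by linear regression or Spearman correlation. Run OPLS with the continuous PK value as the response. Form no high and low PK groups.
- **Independent outcome groups** (PFS3 yes/no, neuropathy yes/no). As a minor clarification, name the rank-sum (Mann-Whitney) test, as 9.10 does, or a log transformation.
- **Within-patient change before and after treatment.** Keep the signed-rank test for this use and say so.

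If the separate document already says this, it is enough to bring 9.9 into line with it. The cost is a few lines of text; samples, assays and data stay the same.
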